#### **Statistical Analysis Plan**

The primary goal of the proposed open trial was to inform the revision of the adapted intervention to be used in the pilot RCT, while the primary goal of the pilot RCT was to inform the design of future appropriately powered trials. As such, we acknowledged that the pilot RCT was underpowered for complex statistical inferences. Instead, sample size for the pilot RCT was determined based on published guidance by Whitehead et al., of 10 to 20 participants per arm for pilot studies with a targeted small effect size. Consistent with expert recommendations, we did not rely on one data point but rather a convergence of data to determine if it was feasible and clinically meaningful to pursue further examination of this intervention. Decisions concerning future development relied upon several factors, including treatment adherence, statistical and clinical significance of outcomes, effect size estimates, treatment satisfaction, and dropout rate.

Acceptability/feasibility. Descriptive statistics were used to inspect participant attendance, homework completion, and parent satisfaction measures (TAI), as well as treatment integrity and fidelity for the intervention. Scores of 80% or higher on percentage of treatment components delivered were considered evidence of feasibility for the delivery of the treatment. These thresholds were based on attendance rates recorded for previous SRPP groups and other group-based PCIT treatments, as well as typical treatment fidelity score targets for standard PCIT.

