# **Study Design**

The study took place over two years and was divided into two phases. In phase 1, we developed a manual to infuse SRPP with key screen time intervention components without extending the length of the intervention or reducing the focus on externalizing behavior problems. We developed detailed session guides, parent handouts, and revised fidelity checklists. Following development, we conducted an open trial with 10 families recruited from participants of a summer camp for children with behavior disorders (Summer Academy). The Summer Academy program runs for 8 weeks (June-August) each summer and includes a once weekly (on Wednesdays) parent intervention group using the SRPP model. Parents choose to participate in a morning group (after child drop-off) or an afternoon group (before child pickup). Open trial participants participated together in one group on Wednesday morning (the more popular time slot in past years of Summer Academy), simultaneously and for the same length of time as the original parenting groups (1.5-hour group sessions weekly over 8 weeks). We

collected data on feasibility, fidelity, and parent satisfaction, as well as pre-, post-, and 1-month follow-up measures of child screen media use and parent behavior. The manual was revised based on feedback from parents and expert consultants. In phase 2, we conducted a pilot RCT using the revised manual by randomly assigning 20 families to receive the adapted intervention and 20 families to the control group receiving the original SRPP. Two pairs of clinicians with master's level training, supervised by Co-I [name], led each group. The intervention for both study arms was delivered in 1.5-hour group sessions weekly for 8 weeks, with parents within each arm choosing whether to attend a morning or afternoon session. Group composition within each arm could change week to week, consistent with the standard practice for Summer Academy. Group size in each session was approximately 10 parents. We offered makeup group sessions later in the same week for parents who missed the weekly session, consistent with the standard practice for Summer Academy.

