# Intervention

The screen time adapted parenting intervention was an adaptation of the School Readiness Parenting Program (SRPP), which is an 8-week evidence-based parenting program for parents of preschool-aged children with externalizing behavior problems. The SRPP is designed to target child externalizing behavior problems specifically, as well as to help parents promote their children's school readiness skills (early academics and social-emotional/behavioral functioning). The SRPP contains traditional aspects of behavioral management strategies (e.g., improving parenting skills and the parent-child relationship; discipline strategies such as time out) that have historically been implemented and found efficacious in behavioral parenting intervention programs. The SRPP follows a group Parent-Child Interaction Therapy (PCIT) model and also uses motivational interviewing and modeling problem-solving approaches. The SRPP utilizes a large group format (10-15 parents) with weekly sessions lasting 1.5 hours. Parents received initial didactic information on skills involving positive parent-child interaction (i.e. the childdirected interaction or "special time" skills) and use of effective commands and time out for discipline (i.e. parent-directed interaction). Parents then broke into subgroups of 3-4 parents for skill practice. During subgroup activities, parents practiced their newly acquired skills with their own children while the other parents in the subgroup observed, recorded, and provided feedback on the parents' performance. Parents rotated through actually practicing the skills and serving as the observers. In this manner, parents were being trained in how to be the "therapist" in terms of knowing what to look for, providing feedback, and then trying the skill themselves. The therapist's role during these subgroup activities was to help the parents who were observing as well as provide feedback to parents who were practicing their skills. In addition to a focus on improving the parent-child relationship and reducing externalizing behavior problems, specific sessions of the SRPP also directly targeted parental interactions during children's learning activities. Setting up homework and household structure and routines to support behavioral and academic functioning (e.g., through good sleep hygiene) was also addressed. In its original form, SRPP did not address management of children's screen time.

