To adapt the SRPP intervention, we first reviewed the literature on how screen media use affects children's behavior and academic outcomes, as well as previous screen media interventions, to guide the content of the adapted parenting intervention. Four major themes were identified: (1) setting screen media routines, (2) monitoring and limiting screen time, (3) choosing educational content, and (4) encouraging positive caregiver-child media interactions. Changes were made to session objectives and materials to include these themes without lengthening sessions. For example, screen media was integrated into discussions on reward systems and behavioral strategies like differential attention. Key adaptations included: (1) using media-relevant examples for behavioral principles, (2) adding discussions on media routines alongside other daily routines (e.g., sleep), and (3) incorporating media-related check-ins during existing progress reviews.

Experts in child media use and parenting reviewed both the initial draft of the intervention protocol and the results of the open trial and changes were made based on their suggestions. Changes made included adding content around caregiver modeling of healthy screen habits, addressing the harms of using media to soothe children, and discussing developmental changes in media routines. The revised intervention protocol was then used for the pilot RCT, with the original SRPP curriculum serving as the control condition.

The parent group for the open trial was led by a master's-level clinician with previous experience as a group leader of SRPP, along with Co-PI [name], who had extensive experience delivering parent training interventions. Before the open trial, Co-PI [name] and the clinician attended the clinician trainings for SRPP held before the start of Summer Academy each year, with Co-I [name] (co-developer of the SRPP). Co-PI [name], the clinician, and Co-I [name] also met for 4 additional hours of training before the start of the open trial to review and discuss the adaptations to the SRPP program in the adapted manual, and weekly during the open trial for supervision. Any potential adaptations to the SRPP training needed in addition to the adapted session guides were noted at this phase for use in the pilot RCT. For the pilot RCT, two master's level clinicians with experience delivering parent training interventions were recruited to lead the

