## **Outcomes and Assessment**

Study outcomes were assessed in both trials at a baseline (pretest), posttest (immediately after the 8-week intervention), and approximately 2 months following the end of the intervention (follow-up0. The primary caregivers were compensated \$25 at the baseline timepoint, \$50 at the posttest timepoint, and \$45 at the follow-up time point for their completion of measures. Caregivers in the open trial who completed an additional semi-structured interview were compensated \$50. The pre- and post-test questionnaire measures were completed by parents during intake and exit appointments with Summer Academy. Families were contacted 1 month after the post-test to complete measures online or by phone, to avoid the burden of an in-person appointment.

**Program feasibility and satisfaction.** We used measures of parent enrollment, attendance at sessions and homework completion between sessions, and clinician adherence to the protocol coded from videotapes to assess feasibility. Parent satisfaction was measured using the Treatment Attitude Inventory (TAI), which is a widely used measure of satisfaction with parenting programs. The TAI was administered at the posttest. Caregivers in the open trial were additionally invited to complete a semi-structured interview about their experiences and thoughts on the adapted intervention at the follow-up time point.

**Screen media use patterns.** At each time point, caregivers were asked to report for the most recent weekday and the most recent weekend day: (1) the child's total amount of screen time, (2) the proportion of screen media content that the child watched that was educational (3) the shows, movies, or apps used; and (4) whether the parent co-used screen media with the child on those days. Caregivers in the open trial were also asked to submit screenshots of the app use summary page from the inbuilt Screen Time (iOS) or Digital Wellbeing (Android) tools of any device the child used, from which information about total daily use of that device and the name and duration of each app used over the previous week (7 days) was gathered. They received \$10 for each set of screenshots (up to \$30 over all timepoints).

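### The 80% feasibility mark has no separate score for the screen-time components, so reaching it does not show that the adaptation was delivered

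*Combined protocol and SAP*

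**What the plan says.** The Acceptability/feasibility paragraph of the Statistical Analysis Plan gives one cut-off: "Scores of 80% or higher on percentage of treatment components delivered were considered evidence of feasibility for the delivery of the treatment". It explains the choice by attendance in past SRPP and other group PCIT programmes, "as well as typical treatment fidelity score targets for standard PCIT". Under Outcomes and Assessment, one of the feasibility measures is "clinician adherence to the protocol coded from videotapes to assess feasibility".

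On what was adapted, Study Design says the aim was to "infuse SRPP with key screen time intervention components without extending the length of the intervention or reducing the focus on externalizing behavior problems". The Intervention section adds: "Changes were made to session objectives and materials to include these themes without lengthening sessions". The additions are media-based examples of behavioural principles, discussion of media routines, and "incorporating media-related check-ins during existing progress reviews". On the comparator it says: "In its original form, SRPP did not address management of children's screen time".

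On the instrument, Study Design says: "We developed detailed session guides, parent handouts, and revised fidelity checklists". The documents give neither the number of items nor their weights, do not say how many items concern screen time, and mention no sub-scores.

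**The concern.** Objective 2 asks whether the screen time adapted intervention is feasible. SRPP is described as an established, evidence-based programme, so the open question is whether the added content can be delivered inside sessions of unchanged length. An overall percentage does not answer that, because it gives credit for shared SRPP items that are also in the control programme. Nor was the cut-off set with the new content in mind: its stated basis is SRPP and PCIT experience, and SRPP did not cover screen-time management.

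The pilot is meant to inform a later, adequately powered trial. A pass on the overall score could be carried forward as evidence that the adaptation fits, although the score alone does not show it. Small between-arm differences would also be harder to interpret if delivery of the distinguishing content were unknown.

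**Working it through.** The 80% is a chosen cut-off, so there is no derived figure to reproduce. The check is how much screen-time content an overall 80% guarantees.

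**Inputs**
- Cut-off: 0.80 (Statistical Analysis Plan).
- *s*, the screen-time share of checklist items: not in the documents; assumed, 10% to 50%.
- *c*, the share of shared SRPP items delivered: not in the documents; assumed, 90%, 95% and 100%.
- *m*, the share of screen-time items delivered: solved for.
- Structure: one pooled score, equal item weights, and screen-time items scored separately from SRPP items. This is the natural reading of the rule but is not stated.

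**Step 1. Formula.** Overall score = (1 − s)·c + s·m. The smallest *m* that still reaches the mark is

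m_min = max(0, [0.80 − (1 − s)·c] / s).

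**Step 2. Result that does not need the value of *s*.** Before truncation at zero, m_min − 0.80 = (1 − s)(0.80 − c)/s. This is negative whenever c is above 80% and s lies between 0 and 100%. So an overall pass never guarantees 80% of the screen-time content once SRPP delivery exceeds 80%.

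**Step 3. Size for assumed values.** For example, at s = 30%:
- c = 100%: (0.80 − 0.70)/0.30 = 33%.
- c = 90%: (0.80 − 0.63)/0.30 = 57%.

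Minimum screen-time delivery that still passes:

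| s | c = 100% | c = 95% | c = 90% |
|---|---|---|---|
| 10% | 0% | 0% | 0% |
| 15% | 0% | 0% | 23% |
| 20% | 0% | 20% | 40% |
| 25% | 20% | 35% | 50% |
| 30% | 33% | 45% | 57% |
| 40% | 50% | 57.5% | 65% |
| 50% | 60% | 65% | 70% |

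**Step 4. When the mark can be met with no screen-time content.** Setting m = 0 gives s ≤ 1 − 0.80/c:
- c = 100%: s ≤ 20%.
- c = 95%: s ≤ 15.8%.
- c = 90%: s ≤ 11.1%.

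For delivery of at most a quarter of the screen-time items to pass with c = 100%, s ≤ 0.20/(1 − 0.25) = 26.7%.

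**Step 5. With a separate 80% mark on the screen-time items,** m must be at least 80% whatever *s* and *c* are.

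**The case against.** Several points on the other side stand.

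- **Pooling is a reading, not a statement.** The fidelity checklists were revised with the manual and are not reproduced. They may already contain a screen-time section.
- **Separable items are an assumption.** Much of the new material sits inside existing activities. If an item fails when its media part is left out, the table does not describe this checklist.
- **The 80% score is not a sole gate.** The plan treats it as evidence and bases decisions on a convergence of adherence, outcomes, effect sizes, satisfaction and dropout. That softens the consequence but does not close the gap: apart from adherence, which is what this score measures, none of these shows whether screen-time content was delivered.

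A reader might also infer three stronger things that the documents do not support.

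- *That the adapted arm can pass with little or none of its new content.* That needs a screen-time share of roughly 20% to 27% or less together with near-complete SRPP delivery. Neither is documented. Integration into existing sessions makes a small share plausible, but four themes spread across the programme could give a larger one.
- *That the new content was the part most likely to be dropped.* No section says so. The adaptation was tried in an open trial and revised, and two clinicians were recruited to lead the adapted groups.
- *That screen-time content leaked into the control arm.* Different clinicians led the two arms, and the control curriculum did not cover the topic. No check of control sessions is described, but absence of a check is not evidence of leakage, and a delivery rule is not a test of differentiation.

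**Conclusion.** The concern holds in a limited form. The plan's only numeric feasibility rule does not isolate the components that make the adapted arm different. Read as one overall score, it can be met with less than 80% of them delivered whenever SRPP delivery exceeds 80%. That conclusion rests on the pooled reading and on separately scored, equally weighted items, but not on any particular screen-time share.

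The size of the shortfall does depend on that share. Over the assumed range, the guaranteed minimum runs from nothing (share of 20% or less with full SRPP delivery) to 70% (share of 50% with 90% SRPP delivery). The documents do not locate the trial within this range, so the claim that the mark could be met without the adaptation must stay conditional. This is a cheap improvement to a stated rule; it does not show that delivery failed.

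**What to change.** In the adapted arm, report fidelity as two figures, one for the screen-time components and one for the shared SRPP components, each with its number of items. Keep the overall score, but count delivery of the adaptation as feasible only if the screen-time sub-score also reaches 80%. State how an item with an embedded media element is scored when that element is left out.

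This uses the revised checklists and the videotape coding already planned. If the checklists already separate the two kinds of item, it is a sentence in the plan and a line in the results table. The documents describe the study in the past tense, so if the tapes have already been scored, the sub-score criterion should be labelled as added afterwards. The price is a sub-score based on fewer items, hence noisier, and possibly a less favourable result.

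Optionally, if control sessions were taped (the documents do not say), report the percentage of screen-time items seen there as a descriptive differentiation check. This is not free: a morning and an afternoon group over 8 weeks at 1.5 hours is up to 2 × 8 × 1.5 = 24 hours of tape, before makeup sessions. The main fix does not depend on it.
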